5.6.4 Loss to follow-up

For subjects whose status is unclear because they fail to appear for study visits without stating an intention to discontinue or withdraw, the investigator must show "due diligence" by documenting in the source documents steps taken to contact the subject, e.g. dates of telephone calls, registered letters, etc. A subject cannot be considered as lost to follow-up until the time point of his/her scheduled end of study visit has passed.

5.6.5 Early study termination by the sponsor

The study can be terminated by Novartis at any time for any reason.

Reasons for early termination:

- Unexpected, significant or unacceptable safety risk to subjects enrolled in the study
- Decision based on recommendations from applicable board(s) after review of safety and efficacy data
- Discontinuation of study drug development

In taking the decision to terminate, Novartis will always consider subject welfare and safety. Should early termination be necessary, subjects must be seen as soon as possible and treated as a prematurely withdrawn subject. The investigator may be informed of additional procedures to be followed in order to ensure that adequate consideration is given to the protection of the subject's interests. If the study is terminated prematurely the investigator or treating physician must ensure appropriate ongoing care is provided to the patient. The investigator will be responsible for informing IRBs/IECs of the early termination of the trial.

6 Visit schedule and assessments

Table 6-1 lists all of the assessments/actions and indicates with an "X" or "S" at which visits they are performed.

Subjects must be seen for all visits on the designated day, or as close to it as possible. Missed or rescheduled visits should not lead to automatic discontinuation. Subjects who prematurely discontinue from the study should have at the time of discontinuation all of the assessments listed for the End of Treatment Week 16 visit, and a Follow-up Week 20 visit. All e-diaries and devices and study medication must be returned to the site at this visit. At this final visit, all dispensed investigational product should be reconciled and the adverse event and concomitant medications reconciled on the CRF.

Subjects should be reminded to be fasting for at least 3 hours before the visits and to bring their medication and their e-diaries. They should not eat at least until the last ECG is performed.

Novartis	
Amended Protocol Version 03 (clean)	

Period	Screening	Treatment					Follow-up (EOS/PSW)	Unplanned		
Visit Day	-28 to -1	1	15	29	43	57	85	113 ¹	141	-
Weeks	-4 to -1	0	2	4	6	8	12	16	20	0
Informed consent	Х									
Demography, AD medical history, Medical history/current medical conditions, Smoking history	х									
Inclusion / Exclusion criteria	Х	Х								
Randomization		Х								
Physical Examination	S	S	S	S	S	S	S	S	S	S
Electrocardiogram (ECG) ²	Х	X (predose AND 2h postdose) ³	х	X (predose AND 2h postdose) ³	Х	x	Х	X³	x	x
Vital Signs	Х	Х	Х	Х	Х	Х	Х	Х	Х	Х
Body Height	Х									
Body Weight	Х	Х		Х		Х	Х	Х	Х	
Hepatitis screen, HIV screen	Х									
Hematology, Clinical Chemistry, Urinalysis	х	х	х	х	Х	х	х	х	х	Х
	1									
Pregnancy Test (Serum)	Х	Х		Х		Х	Х	Х	Х	
Pregnancy Test (Urine)		S								
	8									
Concomitant medications/ Surgical or Medical Procedure	Х	х	Х	X	Х	x	x	Х	x	x
Adverse Events	Х	Х	Х	Х	Х	X	Х	Х	Х	Х

Table 6-1Assessment Schedule

Period	Screening	ening Treatment Follow-up (EOS/PSW)							Unplanned	
Visit Day	-28 to -1	1	15	29	43	57	85	113 ¹	141	-
Weeks	-4 to -1	0	2	4	6	8	12	16	20	0
Patient e-Diary daily entry ⁴					Х					
Patient e-Diary Review		Х	Х	Х	Х	Х	Х	Х	Х	Х
IGA, EASI (incl. BSA),	х	х	x	x	х	x	х	х	x	х
Drug dispensation ⁵		Х		Х		Х	Х			
Drug accountability				Х		Х	Х	Х		
Dosing at site ⁶		Х	Х	Х	Х	Х	Х			
Study Disposition	X									

¹Visit must be the day after the last day of dosing i.e. Day 113; End of treatment visit (EOT) or treatment discontinuation (TD)

²All ECGs are to be performed under fasted conditions (subjects should fast at least 3 hours before the site visit and remain fasted until the last ECG is done). ECG should be done after 10 min rest in supine position, followed by vital signs while supine and then blood samples

³Triplicate standard 12-lead ECGs will be performed at: Baseline (triplicate before intake of drug and triplicate 2 hours post dose), Week 4 (triplicate before intake of drug and triplicate 2 hours post dose), and at Week 16 (triplicate before intake of drug). Single standard ECGs should be done at all other visits.

⁴Starting 1 week prior to Baseline. The investigational site staff must make a phone call to the patient to remind them to switch on the device and start completion. Patient e-Diary will include daily use of emollients, study drug and rescue therapy (if any).

⁵Subjects should be instructed to take study medication every day at the same time preferably in the morning except on study visit days. The subject will record the intake of study medication on a daily basis on the subject e-diary.

⁶ On days of a study visit, subjects should not take the investigational treatment at home; instead they will take it when instructed by study personnel at the investigational site

Note: The use of a bland emollient is required throughout the study and to be applied once a day on the entire body. Subjects should use the same emollient throughout the study. To allow adequate assessment of skin dryness, emollient should not be applied on the area(s) of non-lesional skin designated for such assessments for at least 8 hours before each clinic visit. Tube/container of rescue medication (if any; only when medically justified) will be weighed at the time of dispensing and at every subsequent visit while the rescue medication is used and the weight used recorded.

Novartis Amended Protocol Version 03 (clean)

Page 42 Protocol No. CZPL389A2203

Confidential

Novartis Amended Protocol Version 03 (clean)			Confidential				Page 43 Protocol No. CZPL389A2203			
Period	Screening			т	reatment				Follow-up (EOS/PSW)	Unplanned
Visit Day	-28 to -1	1	15	29	43	57	85	113 ¹	141	-
Weeks	-4 to -1	0	2	4	6	8	12	16	20	0

Note: Patient reported outcomes must be done before physician assessments (IGA, then EASI and BSA

EOS = End of Study. PSW = Premature study withdrawal. X = will be captured in systems for study data collection; S = source capture only

Amended Protocol Version 03 (clean) Protocol No. CZPL389A2203 Protocol No. CZPL389A2203

6.1 Information to be collected on screening failures

All subjects who have signed informed consent but not entered into the next period will have the disposition, demographics, inclusion/exclusion, informed consent, rescreening, withdrawal of consent (if subject withdrew consent) and serious adverse event (SAE) data collected. Adverse events that are not SAEs will be followed by the investigator or primary care physician and collected only in the source data.

6.2 Subject demographics/other baseline characteristics

Subject demographic and baseline characteristic data to be collected on all subjects include: age, sex, race, ethnicity, smoking history, relevant medical history/family history or current medical condition present before signing informed consent. When possible, diagnoses and not symptoms will be recorded.

Investigators will have the discretion to record abnormal test findings on the medical history CRF whenever in their judgment, the test abnormality occurred prior to the informed consent signature. Information about characteristics and history of subjects' AD including previous treatment received will be collected.

6.2.1 Screening for HIV/Hep B and Hep C

- All subjects will be screened for hepatitis B surface antigen (HBsAg), anti-HBs, and anti-HBc. Subjects testing positive for any of the serologic markers will not be eligible for randomization, with the exception of anti-HBs due to previous vaccination against Hep B (unless vaccination was in the past 3 months). Table 16-1 provides detailed Hep B serology result interpretations.
- Screening for hepatitis C will be based on hepatitis C virus antibodies; if the qualitative test result is positive, it will be verified by a second technique (e.g. HCV RNA quantification)
- Evaluation for HIV seropositivity will be performed, and, if positive, confirmation by a second technique available at the laboratory site, e.g., Western blot.

Appropriate counseling will be made available by the Investigator in the event of a positive finding. Results will be available as source data and will not be recorded within the CRF. All samples will be shipped to the central laboratory.

6.3 Treatment exposure and compliance

6.3.1 ZPL389 / placebo

Study drug compliance will be assessed by the investigator and/or center personnel at designated visits by recording capsule counts from the previously dispensed container. This information should be captured in the source document at each designated visit. All study treatment dispensed and returned must be recorded in the Drug Accountability Log.

Subjects must be requested to record in the e-diary their intake of study medication on a daily basis.

Novartis	Confidential	Page 46
Amended Protocol Version 03 (clean)		Protocol No. CZPL389A2203

Study personnel will review the e-diary entries at each visit for study drug intake and discuss with patient any missed doses. Study personnel will also review the amount of study medication returned by the subject. The total number of doses of study drug intake since the last dispensing visit will be recorded in the appropriate CRF based on the returned study medication and discussion with the patient.

6.3.2 Rescue medication and emollient

Subjects are requested to record in the e-diary their use of emollient. If the subject needed rescue medication and it was dispensed by the investigator, the subject needs to enter rescue medication use on a daily basis in the e-diary.

In addition, Investigators will weigh the rescue medication container at the time of dispensing and at the time of return at the next study visit. The information will be recorded in the appropriate CRF.

6.4 Efficacy

The investigator assessments should be performed by the same member of study site staff throughout the study. Adequate time should be scheduled allowing for a complete examination.

The IGA, EASI, evaluations require a full-body examination - subjects must be undressed. Observations must also be made in a well-lit area.

Assessments performed by the investigator are to be conducted after the subject has completed the on-site reported outcome assessments, and should be performed in the following order: IGA, then EASI

6.4.1 Appropriateness of efficacy assessments

The efficacy measurements are standard for this indication (Eichenfield et al 2014).

6.4.2 IGA

The IGA rating scale is used to determine the severity of AD symptoms and clinical response to treatment. It reflects a subject's overall disease severity for the whole body based on a 5-point scale. The 5-point scale includes: clear, almost clear, mild, moderate, and severe disease. It is a static scale and does not refer to previous status of the subject. The Investigator or trained qualified designee will complete the IGA assessment on each of the visits as outlined in the assessment schedule. Whenever possible, the IGA assessments should be performed by the same evaluator throughout the study. Please, see Section 17 for details.

6.4.3 EASI

The EASI (Eczema Area and Severity Index) will be used to make an assessment of the extent and severity of AD (Hanifin 2001). The Investigator or trained qualified designee will complete the EASI assessment on each of the visits as outlined in the assessment schedule. Whenever possible, the EASI assessments should be performed by the same evaluator throughout the study.

Each body region (head/neck [H], upper limbs [UL], trunk [T], and lower limbs [LL]) will be assessed for:

- Severity of AD: the average degree of the following key signs of AD (erythema, induration/papulation, excoriation, and lichenification) will each be assigned a score of 0, 1, 2 or 3 indicating none (0), mild (1), moderate (2), and severe (3) expression of the clinical sign, as indicated in Table 6-3 EASI: severity descriptions.
- Extent of AD: Based on the extent of AD in a particular body region (when each body region is considered as a whole or 100%), an Area score will be assigned to that body region.

Please note:

- Only inflamed areas should be included in the assessment, dry skin or post inflammatory pigmentation changes should not be included.
- The neck is assessed as part of the head region.
- The axillae and groin are assessed as part of the trunk.
- The buttocks are assessed as part of the lower limbs.

For a calculation of EASI score (ranging from 0 to 72), please see Table 6-4.

Calculation of BSA (total body surface area affected by AD): percentage of each body region affected by AD will be multiplied by its respective body region corresponding factor (0.1 for head, 0.3 for trunk, 0.2 for upper limbs and 0.4 for lower limbs).

Total BSA affected by AD = 0.1xHead area % + 0.2xUpper limbs area % + 0.3xTrunk area % + 0.4xLower limbs area %.

Sign score	Grading	Description
Erythema (E)		
0	None	N/A
1	Mild	Faintly detectable erythema: very light pink
2	Moderate	Dull red, clearly distinguishable
3	Severe	Deep/dark red
Induration / Papula	ation (P)	
0	None	N/A
1	Mild	Barely perceptible elevation
2	Moderate	Clearly perceptible elevation but not extensive
3	Severe	Marked and extensive elevation
Excoriations (Ex)		
0	None	N/A
1	Mild	Scant evidence of excoriations with no signs of deeper skin damage (erosion, crust)
2	Moderate	Several linear marks of skin with some showing evidence of deeper skin injury (erosion, crust)
3	Severe	Many erosive or crusty lesions
Lichenification (L)		
0	None	N/A

Table 6-3EASI: severity descriptions

Novartis		Confidential	Page 48
Amended Protoc	ol Version 03 (c	lean)	Protocol No. CZPL389A2203
1	Mild	Slight thickening of the skin disce markings minimally exaggerated	ernible only by touch and with skin
2	Moderate	Definite thickening of the skin wit that they form a visible crisscross	h skin markings exaggerated so s pattern
3	Severe	Thickened indurated skin with sk exaggerated crisscross pattern	in markings visibly portraying an

Body region	Erythema (E)	Induration / Papulation(P)	Excoriation (Ex)	Lichenification (L)	Area score (A)	EASI calculation
Head &	0=none	0=none	0=none	0=none	0= 0%	(E+P+Ex+L)
neck	1=mild	1=mild	1=mild	1=mild	1= >0 - <10%	x A x 0.1
(H)	2=moderate	2=moderate	2=moderate	2=moderate	2=10% to <30%	
	3=severe	3=severe	3=severe	3=severe	3=30% to <50%	
					4=50% to <70%	
					5=70% to <90%	
					6=90% to 100%	
Trunk	0=none	0=none	0=none	0=none	0=0%	(E+P+Ex+L)
(T)	1=mild	1=mild	1=mild	1=mild	1=>0 - <10%	x A x 0.3
	2=moderate	2=moderate	2=moderate	2=moderate	2=10% to <30%	
	3=severe	3=severe	3=severe	3=severe	3=30% to <50%	
					4=50% to <70%	
					5=70% to <90%	
					6=90% to 100%	
Upper	0= none	0=none	0= none	0= none	0= 0%	(E+P+Ex+L)
limbs	1= mild	1=mild	1= mild	1= mild	1= >0 - <10%	x A x 0.2
(UL)	2=moderate	2=moderate	2=moderate	2=moderate	2=10% to <30%	
	3=severe	3=severe	3= severe	3=severe	3=30% to <50%	
					4=50% to <70%	
					5=70% to <90%	
					6=90% to 100%	
Lower	0=none	0=none	0=none	0=none	0= 0%	(E+P+Ex+L)
limbs	1=mild	1=mild	1=mild	1=mild	1= >0 - <10%	x A x 0.4
(LL)	2=moderate	2=moderate	2=moderate	2=moderate	2=10% to <30%	
	3=severe	3=severe	3=severe	3= severe	3=30% to <50%	
					4=50% to <70%	
					5=70% to <90%	
					6=90% to 100%	
EASI sco	re =					sum of the above 4

Table 6-4 **EASI** calculation

scores

6.5 Safety

In addition to the below listed safety assessments, safety monitoring must be done at every visit as per Section 7 as well as review of concomitant medications with reference to prohibited medications (Table 5-1). The safety assessments and monitoring is in accordance with the risks associated with ZPL389 and/or unknown information.

6.5.1 Physical exam

A physical examination, including general appearance, will be performed at every visit. If indicated, based on medical history and/or symptoms, additional exams will be performed at the discretion of the investigator. If possible, assessments for an individual subject should be performed by the same member of the study site staff throughout the study.

Information for all physical examinations must be included in the source documentation at the study site. Significant findings that are present prior to the subject signing informed consent must be included in the medical history CRF. Significant findings made after the signing of the informed consent which meet the definition of an AE must be recorded on the AE CRF.

6.5.2 Body Weight and height

Body weight (to the nearest 0.1 kilogram [kg] in indoor clothing, but without shoes) will be measured at the visits specified in the table of assessments.

Height in centimeters (cm) will be measured at the visit specified in the assessments schedule.

6.5.3 Electrocardiogram (ECG)

ECGs will be analyzed centrally and performed with ECG machines supplied by the central provider.

ECGs should be done in fasting conditions (subjects should fast for at least 3 hours before the site visit) and after 10 minutes rest in the supine position. The sequence of cardiovascular data collection during study visits is ECG collection first, followed by vital signs and then blood sampling. The Fridericia QT correction formula (QTcF) should be used for clinical decisions.

Standard 12-lead ECGs will be performed as indicated in the assessment schedule; triplicates standard ECG at Baseline, Week 4 and Week 16 visits and single standard ECGs at all other visits. Subjects must remain fasted until the last ECG is performed.

In the event that the central cardiologist reports that an ECG is abnormal, then the investigator must comment as to whether the ECG abnormality is either clinically significant or clinically insignificant. If necessary, a local cardiologist may be consulted.

Clinically significant abnormalities should be recorded on the relevant section of the appropriate CRF.

6.5.4 Vital Signs

Measurements will include pulse rate, supine systolic and diastolic blood pressure.

On visits where an ECG is also being performed, the blood pressure measurement should be done after the ECG measurements while the subject is in the supine position. Pulse rate (heart rate) will be done as part of the ECG measurement, if taken at the visit at which ECG is done.

After the subject has been resting in supine position for approximately 10 minutes, systolic and diastolic blood pressure will be measured twice using an automated validated device, e.g. OMRON, with an appropriately sized cuff. The repeat measurements will be made at 1 to 2 minute intervals and the mean of the two measurements will be used. In case the cuff sizes available are not large enough for the subject's arm circumference, a sphygmomanometer with an appropriately sized cuff may be used.

6.5.5 Laboratory evaluations

A central laboratory will be used for analysis of all blood specimens detailed in this section, unless otherwise specified. Samples will be collected according to the assessment schedule. Details on the collections, shipment of samples, and reporting of results by the central laboratory will be provided to Investigators in the central laboratory manual.

6.5.5.1 Clinical Chemistry

The chemistry panel will include: albumin, alkaline phosphatase (ALP), total bilirubin (TBL), calcium, chloride, total cholesterol, LDL-cholesterol, HDL-cholesterol, creatinine, creatine kinase (CK), aspartate aminotransferase (AST), alanine aminotransferase (ALT), gamma-glutamyltransferase (γ -GT), glucose, sodium, potassium, inorganic phosphorus, total protein, lactate dehydrogenase (LDH), triglycerides, magnesium, blood urea nitrogen (BUN), and uric acid. Estimated creatinine clearance will be calculated using the MDRD formula. Lipase and amylase will be included at Screening and Baseline. PT/INR (Prothrombin time/ International Normalized Ratio) must be included in unscheduled visits.

If the TBL concentration is increased above 1.5 x ULN, direct and indirect reacting bilirubin should be differentiated.

6.5.5.2 Hematology

Hemoglobin, hematocrit, red blood cell count, WBC count with differentials and platelet count will be measured.

6.5.6 Pregnancy Test

For all WOCBP, a serum pregnancy test is required at Screening, Baseline and at monthly intervals during treatment (at scheduled visits). A serum pregnancy test will also be performed at the end of the study. Additionally, at Baseline a urine pregnancy assessment should be done and the result must be evaluated prior to randomization but only captured on source documents.

6.5.6.1 Urinalysis

Dipstick measurements for protein, blood, and WBC/leukocytes will be performed.

If dipstick measurement results are positive (abnormal), results will be captured in the CRF. Microscopy must be assessed following an abnormal dipstick test.

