7.4 Renal safety monitoring

As part of standard renal monitoring, the following two categories of abnormal renal laboratory values have to be considered during the course of the study:

- Serum event:
 - confirmed (after ≥24h) increase in serum creatinine of ≥25% compared to baseline during normal hydration status
- Urine event:
 - new onset (≥1+) proteinuria; confirmed by doubling in the urinary albumin-creatinine ratio (ACR) or urinary protein-creatinine ratio (PCR) (if applicable)
 - new onset (≥1+), hematuria or glycosuria

Every renal laboratory trigger or renal event as defined in Table 15-1 should be followed up by the investigator or designated personnel at the trial site as summarized in Appendix 3.

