9.5.2 Safety variables

All safety endpoints (i.e. adverse events, laboratory data, vital signs, and ECG) will be summarized by treatment for all subjects of the safety set. All data will be included in the analysis regardless of rescue medication use.

Adverse events

Treatment emergent adverse events (events started after the first dose of study treatment or events present prior to the first dose of study treatment but increased in severity based on preferred term; AEs observed four weeks after last study-drug administration will not be considered as treatment-emergent) will be summarized. AEs will be summarized by presenting, for each treatment group, the number and percentage of subjects having any AE, having an AE in each primary system organ class and having each individual AE (preferred term). Summaries will also be presented for AEs by severity and for study treatment related AEs. If a subject reported more than one adverse event with the same preferred term, the adverse event with the greatest severity will be presented. If a subject reported more than one adverse event with the subject will be counted only once with the greatest severity at the system organ class level, where applicable.

Serious adverse events will also be summarized.

Separate summaries will be provided for deaths, serious adverse events, and other significant adverse events leading to discontinuation.

Non-treatment emergent adverse events will be reported separately.
Laboratory data

The summary of laboratory evaluations will be presented for two groups of laboratory tests (hematology and serum chemistry). Descriptive summary statistics for the change from baseline to each study visit will be presented. These descriptive summaries will be presented by test group, laboratory test and treatment group. Change from baseline will only be summarized for subjects with both baseline and post baseline values. Shifts with respect to normal ranges and number and percentage of notable abnormalities will also be summarized. For each parameter, the maximum change from baseline will be analyzed analogously.

Vital signs

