10.5 Quality Control and Quality Assurance

Novartis maintains a robust Quality Management system that includes all activities involved in quality assurance and quality control, including the assignment of roles and responsibilities, the reporting of results, and the documentation of actions and escalation of issues identified during the review of quality metrics, incidents, audits and inspections.

Audits of investigator sites, vendors, and Novartis systems are performed by Novartis Pharma Auditing and Compliance Quality Assurance, a group independent from those involved in conducting, monitoring or performing quality control of the clinical trial. The clinical audit process uses a knowledge/risk based approach.

Audits are conducted to assess GCP compliance with global and local regulatory requirements, protocols and internal standard operating procedures, and are performed according to written Novartis processes.

11 **Protocol adherence**

This protocol defines the study objectives, the study procedures and the data to be collected on study participants. Additional assessments required to ensure safety of subjects should be administered as deemed necessary on a case by case basis. Under no circumstances including incidental collection is an investigator allowed to collect additional data or conduct any additional procedures for any purpose involving any investigational drugs under the protocol, other than the purpose of the study. If despite this interdiction, data, information, observation would be incidentally collected, the investigator shall immediately disclose it to Novartis and not use it for any purpose other than the study, except for the appropriate monitoring on study participants.

Investigators ascertain they will apply due diligence to avoid protocol deviations. If an investigator feels a protocol deviation would improve the conduct of the study this must be considered a protocol amendment, and unless such an amendment is agreed upon by Novartis and approved by the IRB/IEC and health authorities, where required, it cannot be implemented.

11.1 **Protocol Amendments**

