# 2.7.3 Laboratory data

Abnormal laboratory results that meet the criteria for adverse events will be summarized as part of the AE reporting.

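### New-onset glycosuria is a renal alert in Protocol 7.4, but no urine test named in the protocol measures glucose

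*Protocol*

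**What the plan says.** Protocol 7.4 (Renal safety monitoring) sets out serum and urine events. The urine events are new-onset proteinuria of 1+ or more, confirmed by ACR or PCR where applicable, and "new onset (≥1+), hematuria or glycosuria". It then requires action: "Every renal laboratory trigger or renal event as defined in Table 15-1 should be followed up by the investigator" or site staff, as laid out in Appendix 3.

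Protocol 6.5.6.1 (Urinalysis) defines the routine urine test: "Dipstick measurements for protein, blood, and WBC/leukocytes will be performed". An abnormal dipstick leads to microscopy. No other reflex test is given there.

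The assessment schedule (Table 6-1) has a single row, "Hematology, Clinical Chemistry, Urinalysis", marked at every visit, with no analytes listed. Glucose is in the blood chemistry panel of Protocol 6.5.5.1 ("glucose, sodium, potassium, inorganic phosphorus, total protein") and appears again as a fasting blood test among the follow-up actions in Table 15-1.

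**The concern.** An alert defined on a dipstick grade needs a dipstick pad that reads it. To call a finding new, it also needs a reading before treatment. Protein and blood have both. Glucose has neither in the tests the protocol names.

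What is at stake is a prompt to the investigator. A patient who developed glycosuria with normal blood glucose would raise no flag from the scheduled tests, although the protocol classes the finding as a renal event. There is also a risk in interpretation: an absence of glycosuria alerts could be taken as reassuring when nothing specified could have produced one.

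No planned table would be false as a result. Protocol 9.5.2 limits laboratory summaries to hematology and serum chemistry, and SAP 2.7.3 says "Abnormal laboratory results that meet the criteria for adverse events will be summarized as part of the AE reporting". The SAP's further tables in 2.7.1.1 concern QTc and liver events, not urine.

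**Working it through.** The plan states no figure to reproduce. The check compares the alerts with the tests, then counts the visits and patients concerned.

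**1. Alerts against tests**

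| Dipstick alert (Protocol 7.4) | Matching analyte (Protocol 6.5.6.1) |
|---|---|
| Proteinuria, 1+ or more | protein |
| Hematuria, 1+ or more | blood |
| Glycosuria, 1+ or more | none |

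Two of three alerts are covered; one is not.

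**2. Other urine tests named in the protocol**

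- Microscopy (6.5.6.1): follows an abnormal dipstick and is not a glucose assay.
- Urine pregnancy test at Baseline (6.5.6): not relevant.
- ACR and PCR (7.4, Table 15-1): measure albumin or protein against creatinine.

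None measures glucose. The two places where glucose is measured (6.5.5.1 and the Table 15-1 follow-up) both use blood.

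**3. Visits concerned (Table 6-1)**

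Urinalysis is scheduled at screening and on Days 1, 15, 29, 43, 57, 85, 113 and 141, which is 9 visits, plus unplanned visits. Taking the Day 1 sample as pre-dose, 2 visits could give the baseline and 9 − 2 = 7 could show new onset. Patients who enter the extension do not attend the Day 141 follow-up (Protocol 3.1 and 5.6.1), so they have 7 − 1 = 6.

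**4. Patients concerned**

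The documents give no rate of new glycosuria. The rates below are assumptions, used only to show scale. Patients on ZPL389: 45 + 45 + 90 + 90 = 270.

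| Assumed rate | All planned (360 × rate) | ZPL389 arms (270 × rate) |
|---|---|---|
| 0.5% | 1.8 | 1.35 |
| 1% | 3.6 | 2.7 |
| 2% | 7.2 | 5.4 |

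These are upper limits for each rate. SAP 3 says the final sample is below 360, and patients with raised blood glucose as well would be noticed through the chemistry panel.

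**The case against.** The strongest reply is that little is lost. As far as the extracted layout of Table 15-1 can be read, a glycosuria alert would lead to fasting blood glucose, serum creatinine and ACR. Glucose and creatinine are already drawn at every visit, and patients are asked to fast for at least 3 hours beforehand (Protocol 6). On that reading only ACR and the prompt itself go missing. The risk section (Protocol 3.6) describes no renal signal, and entry requires an estimated GFR of at least 60. This stands, and it is why the point is minor. It does not close the gap, because blood glucose is not the criterion in Section 7.4 and cannot show glycosuria when it is normal.

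A second reply is that the list in 6.5.6.1 may simply be incomplete. Table 15-1 seems to treat glycosuria as a dipstick finding, and the laboratory manual, which was not available, might specify a strip with a glucose pad. That cannot be excluded. But the list is worded as complete, and an alert criterion does not specify a test. The Table 15-1 row is garbled in the extracted text, so the point rests on Section 7.4, which is intact.

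Third, other alerts also go beyond the scheduled panels: INR for liver events, and ACR and PCR for renal events. Those tests are at least named in the protocol; urine glucose is not. Protocol 11 does allow extra safety tests ("Additional assessments required to ensure safety of subjects should be administered as deemed necessary on a case by case basis"), so glycosuria could be found that way. Tests ordered on occasion do not, however, provide a systematic baseline or a routine post-baseline check.

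Finally, the assumed rates of 0.5% to 2% have no source in the documents. That is correct; the inconsistency does not depend on them.

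**Conclusion.** The concern holds. Sections 6.5.6.1 and 7.4 disagree, and one of the three dipstick alerts cannot be triggered by any urine test the protocol specifies. The defect is minor and confined to safety monitoring; the primary and secondary efficacy analyses, the sample size and the error rates do not change.

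Its practical size is probably a few patients at most: about 2 to 7 of 360 planned, or about 1 to 5 of the 270 planned on ZPL389, if the true rate lies between 0.5% and 2%. The conclusion assumes that the dipstick used contained only the listed analytes. If the laboratory's strip included glucose and sites saw the result, the fault is in the protocol text alone.

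**What to change.** Add glucose to the dipstick analytes in Protocol 6.5.6.1 at all scheduled urinalysis visits, including screening and Baseline. The cost is one word and one analyte on a dipstick already being done, with no extra visit or sample. ACR and PCR can stay as confirmatory tests outside the scheduled panel.

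If urine glucose is not wanted, delete glycosuria from Section 7.4 and remove the matching row of Table 15-1 after checking it in the source document.

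Since the trial has stopped, the useful step now is to ask the laboratory whether urine glucose was recorded. If it was not, the study report should not present the absence of glycosuria alerts as evidence that none occurred, and the text should be corrected before it is reused in another protocol.
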